8.2. Adverse Events

AEs will be classified using the Medical Dictionary for Regulatory Activities (MedDRA) system organ classes and preferred terms. MedDRA version 15.0 will be used throughout the study. All AEs will be listed.

In general, AEs will be analyzed based on *incidence*, defined as the proportion of subjects who had at least one occurrence of an event out of the number of subjects in the Safety Analysis Set.

All AE listings will include the onset and resolution study days relative to 9HB01EXT Study Day 1. AEs that are emergent during a major surgical/rehabilitation period, AEs that are emergent on the day of surgery, and AEs that occur during the gap of greater than 14 or 7 days will be flagged. In addition, a separate listing will be provided for AEs that are emergent during a major surgical/rehabilitation period.

AEs occurring during a major surgical/rehabilitation period with an onset date on the day the surgical/rehabilitation period starts or on the day of the surgery will be included in the summaries of the study AEs but excluded from the summaries or listings of AEs occurring during a major surgical/rehabilitation period. Consideration is given to AEs with an onset date at the start of the surgical/rehabilitation period in the event the pre-surgical dose was administered the day before the surgery.

Events of overdose will not be included in the AE summary tables unless they are reported as AEs.

The algorithm for the determination of AEs that are emergent during a major surgical/rehabilitation period, AEs with an onset date on the day of the surgical/rehabilitation period starts or on the day of the surgery, and AEs that are emergent during a treatment regimen period when an onset date is partially or completely missing is described below.

- If the onset date of an AE is present, then the date of onset will be compared with the start/stop dates of the major surgical/rehabilitation period and treatment regimen period to determine whether the AE is during a major surgical/rehabilitation period, on the day of the surgical/rehabilitation period starts, on the day of the surgery, or during a treatment

regimen period. If the onset of the AE is on the day of the treatment regimen change, then it will be attributed to the previous treatment regimen.

- If the onset day of an AE is missing and the onset month and year of the AE are completely within a major surgical/rehabilitation period or a treatment regimen period, then the AE will be attributed to that major surgical/rehabilitation period or that treatment regimen period. For example, the onset of an AE is recorded as 2013-03. A major surgical/rehabilitation period for that subject needs to cover at least from 00:01 on the later date of 2013-03-01 and 9HB01EXT Study Day 1 to 23:59 on the earlier date of 2013-03-31 and the end of his safety period for that AE to be attributed to that major surgical/rehabilitation period. Similarly, if the start and stop time of a treatment regimen do not completely cover the possible range of the onset of AE, then the treatment regimen for that AE will be set to unknown. Regardless of the above, the AE will not be attributed to the day the major surgical/rehabilitation period starts or the day of the major surgery because the exact date is missing.
- If the onset day and month of an AE are missing and the onset year of the AE is completely within a major surgical/rehabilitation period or a treatment regimen period, then the AE will be attributed to that major surgical/rehabilitation period or that treatment regimen period. For example, the onset of an AE is recorded as 2013. A major surgical/rehabilitation period for that subject needs to cover at least from 00:01 on the later date of 2013-01-01 and 9HB01EXT Study Day 1 to 23:59 on the earlier date of 2013-12-31 and the end of his safety period for that AE to be attributed to that major surgical/rehabilitation period. Similarly, if the start and stop time of a treatment regimen do not completely cover the possible range of the onset of AE, then the treatment regimen for that AE will be set to unknown. Regardless of the above, the AE will not be attributed to the day the major surgical/rehabilitation period starts or the day of the major surgery because the exact date is missing.
- If the AE onset date is completely missing, the AE will be considered to be outside any major surgical/rehabilitation period and the treatment regimen for that AE will be set to unknown.

8.2.1. Overall Summary of Treatment-emergent Adverse Events

An overall summary of treatment-emergent adverse events (TEAEs) will be provided which tabulates the number and percentage of subjects who experienced a TEAE, related TEAE, treatment-emergent SAE, or treatment-emergent related SAE; the number and percentage of subjects who discontinued treatment or withdrew from the study due to an AE; and the number and percentage of subjects who died. This table will also be presented by subgroup based upon contemporaneous entry compliance of $\geq 80\%$, as described in Section 6.5.5.3.

AEs that occurred during major surgical/rehabilitation periods will be included in the overall summary of AEs (in the surgery subgroup column) but not in any of the other AE summary tables.

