If the treatment regimen after the surgical/rehabilitation period is a prophylactic regimen, then the end of the surgical/rehabilitation period is:

- 1 minute before the first prophylactic dose on or after the last date among the dates for discharge from the hospital, post-operative visit 1, post-operative visit 2, the end of rehabilitation.
- If all of the dates mentioned above are missing, then select the first prophylactic dose after the date/time for the end of surgery. If the surgery time was not recorded or recorded as 00:00, then select the surgery date and impute 23:59 for the time. If the end date of the surgery is missing, then select the start date of the surgery and impute 23:59 for the time.
- If there are no prophylaxis doses following the latter of the 6 dates mentioned above, then select the latter of the dates and impute 23:59 for the time if otherwise there is no time associated with the given date (e.g., the subject completed the surgical/rehabilitation period but received no further prophylactic doses).
- If the overall end of study is declared while the subject is still in the surgical/rehabilitation period, then select the date of the end of study and impute 23:59 for the time.

If the treatment regimen after the surgical/rehabilitation period is the episodic regimen, then the end of the surgical/rehabilitation period is:

- Imputed as 23:59 on the last date among the dates for discharge from the hospital, post-operative visit 1, post-operative visit 2, and the end of rehabilitation
- If all of the dates mentioned above are missing, then select the date of the end of surgery and impute 23:59 for the time. If the end date of the surgery is missing, then select the start date of the surgery and impute 23:59 for the time.

Two exceptions are noted:

- If 2 (or more) major surgeries are performed without an intervening discharge from the hospital, then the first surgical/rehabilitation period will end 1 minute before the

start of the next surgery and the second surgical/rehabilitation period will end as described above.

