8.2.2. Treatment-emergent Adverse Events

In general, an AE will be regarded as treatment-emergent if it was present prior to receiving the first injection of rFIXFc in the parent study and subsequently worsened in severity, or was not present prior to receiving the first injection but subsequently appeared before the subject's last visit on study or the follow-up phone call, whichever came later (or the date of withdrawal/loss to follow-up).

All AEs that occurred on or after 9HB01EXT Study Day 1 will be considered treatment-emergent in study 9HB01EXT. AEs that were treatment-emergent in the parent studies and carried over to study 9HB01EXT without worsening in severity will be considered the same AEs and will not be counted again in study 9HB01EXT.

The incidence of TEAEs will be summarized by system organ class (SOC) and preferred term. Unless specified otherwise, SOCs and preferred terms within each SOC will be presented alphabetically. For the purpose of summarization, a subject is counted once in a SOC or preferred term if the subject reported one or more events in that SOC or preferred term. Unless specified otherwise, percentages will be based on the number of subjects in the Safety Analysis Set.

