8.2.4. Severity of Adverse Events

AEs are classified by the Investigator for severity ("Mild", "Moderate", and "Severe"). A summary of TEAEs by SOC, preferred term, and severity will be presented. AEs with a missing severity will be counted as "Severe" in the summary table. A subject will be counted once for each SOC and preferred term based on the greatest severity within that SOC and preferred term, respectively.

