8.2.5. Relationship of Adverse Events to Study Drug

AEs are classified by the Investigator for relationship to study drug ("Not related" and "Related"). A summary of TEAEs by SOC, preferred term, and relationship will be presented. AEs with a missing relationship will be counted as "Related" in the summary table. A subject will be counted once for each SOC and preferred term based on the highest relationship within that SOC and preferred term, respectively.

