8.2.6. Serious Adverse Events

Any AE reported as resulting in death, immediate risk of death (life threatening), inpatient hospitalization or prolongation of existing hospitalization, persistent or significant disability/incapacity, or a congenital/anomaly/birth defect will be classified as an SAE by the Investigator. An SAE may also be any other medically important event that, in the opinion of

the Investigator, may jeopardize the subject or may require intervention to prevent one of the other outcomes listed above.

All SAEs will be listed; treatment-emergent SAEs will be summarized by SOC and preferred term.

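### AEs that start after the day of major surgery are left out of the detailed AE tables, so any-event, severe, related and SAE incidences can only equal or fall below the all-TEAE figures

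*SAP*

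**What the plan says.** SAP 8.2.2 sets the scope: "All AEs that occurred on or after 9HB01EXT Study Day 1 will be considered treatment-emergent in study 9HB01EXT". SAP 8.2.1 then says that AEs from major surgical/rehabilitation periods go into the "overall summary of AEs (in the surgery subgroup column) but not in any of the other AE summary tables". The other tables are SOC/PT (8.2.2), descending PT and severe PT (8.2.3), severity (8.2.4), relationship (8.2.5) and SAEs (8.2.6). None of those sections brings the events back. On serious events, 8.2.6 says only: "All SAEs will be listed; treatment-emergent SAEs will be summarized by SOC and preferred term".

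SAP 8.2 makes one exception. AEs with onset on the day the period starts, or on the day of surgery, are "included in the summaries of the study AEs but excluded from the summaries or listings of AEs occurring during a major surgical/rehabilitation period". If an onset date is partial and its whole possible range lies inside the period, "the AE will be attributed to that major surgical/rehabilitation period or that treatment regimen period". Such an event cannot be assigned to the first day or to the day of surgery, so it cannot use the exception. An AE with no onset date at all is treated as outside the period and stays in the tables.

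Percentages use the full Safety Analysis Set (8.2 and 8.2.2). In the severity table a subject is "counted once for each SOC and preferred term based on the greatest severity", and in the relationship table "counted once for each SOC and preferred term based on the highest relationship".

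Protocol 16.6.2 plans AE incidence in total and broken down by severity and relationship, and mentions no surgical exclusion. Protocol 16.4.2 does write one, but only for visit-based efficacy endpoints.

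**The concern.** Long-term safety is the primary objective. A reader of the PT, severity, relationship or SAE table will take its percentages to cover the whole study, because the subjects who had surgery are in the denominator. Their post-operative events are not in the numerator. Subjects may still be receiving study drug in that window, and Protocol 10.1.3 allows doses above 100 IU/kg around surgery.

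The SAE table shows the effect most clearly. Protocol 15.2.3 makes major surgery itself a reportable SAE, and one recorded with onset on the day of surgery stays in the table. The same section names vascular thrombotic events associated with rFIXFc as medically important. Such an event starting after the day of surgery drops out of the SOC/PT table of SAEs. It would still be listed, and it would still count in the surgery column of the overall summary.

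**Working it through.** The plan gives no figure to reproduce, so the check covers which events are removed, the direction of the effect, the weight of one subject and the length of the window.

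**Which events are removed.** Under SAP 5.3.3 the period starts on the day of surgery or the day before. Section 8.2 keeps onsets on both of those days. The fully dated AEs left out are therefore those that start after the day of surgery. Partial dates lying wholly inside the period are left out as well.

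**Direction.** Each incidence is (subjects with at least one qualifying event) / N, with N fixed. Removing events from a subject can take him out of the numerator but never add him. The severity and relationship rows behave differently, because each subject is placed once, at his worst category. Comparing one subject's worst event outside the period with his worst inside it gives:

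| Row | Possible change in count (SAP rule minus all TEAEs) |
|---|---|
| Any event (overall, SOC or PT) | 0 or −1 |
| Severe | 0 or −1 |
| Related | 0 or −1 |
| SAE | 0 or −1 |
| Mild, Moderate, Not related | −1, 0 or +1 |

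The +1 arises when the worst event is removed and the subject drops to a lower category.

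**Weight of one subject**, at the planned sizes in SAP 3.3.1 and Protocol 16.10 (100 + 20 = 120):
- overall: 1/120 = 0.83 percentage points
- 998HB102: 1/100 = 1.0
- 9HB02PED: 1/20 = 5.0

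If 1, 3, 5 or 10 subjects (assumed) had their only qualifying event in the omitted window, the overall understatement would be 0.83, 2.50, 4.17 or 8.33 points.

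**Illustration, with assumed counts.** Ten of 120 subjects have a mild event of one PT outside surgery. One of the ten also has a severe event of that PT after the day of surgery.

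| Row | SAP rule | All TEAEs |
|---|---|---|
| Mild | 10/120 = 8.3% | 9/120 = 7.5% |
| Severe | 0/120 = 0% | 1/120 = 0.83% |
| Any event | 10/120 = 8.3% | 10/120 = 8.3% |

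Now suppose two of 20 children have the mild event and one of those two also has the severe event. The SAP table shows Mild 2/20 = 10.0% and Severe 0%. With all TEAEs it shows Mild 1/20 = 5.0% and Severe 1/20 = 5.0%.

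**Length of the window.** For a subject going back to prophylaxis, SAP 5.3.3 ends the period just before routine dosing resumes, and looks for that resumption from this point onward: "the last date among the dates for discharge from the hospital, post-operative visit 1, post-operative visit 2, the end of rehabilitation". On-demand subjects follow the same dates. Protocol 7.1 requires surgery Visit 3 one to two weeks after major surgery. If that visit is the first post-operative visit of SAP 5.3.3 (assumption), the window lasts at least about 7 to 14 days per surgery. Over the 4-year maximum (4 × 365.25 = 1461 days) this is 7/1461 = 0.5% to 14/1461 = 1.0% of follow-up. Over an assumed single year it is 7/365.25 = 1.9% to 14/365.25 = 3.8%. Rehabilitation can extend it with no stated limit.

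**The case against.** The rule is openly stated and fits a wider convention. The SAP also sets aside major surgical periods for the physician's global assessment, questionnaires, hematology and chemistry, and vital signs. Post-operative events are confounded by the surgery, so showing them apart is a defensible choice, and no passage demands pooling.

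Little is hidden. The surgery column of the overall summary counts subjects with any TEAE, related TEAE, SAE and related SAE, discontinuation or withdrawal due to an AE, and death. The events are flagged in the full AE listing and have a separate listing. SAEs, discontinuations and deaths are also listed. SAP 7.6 calls the surgery subgroup small. Doses above 100 IU/kg are not confined to surgery (Protocol 7.1.1). Table shells exist but are not among the documents, and a footnote there might disclose the exclusion.

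All of this is fair, and it limits the weight of the point. It does not remove it. The SAP's table list has no SOC/PT, severity, relationship or SAE table for the omitted events, so their rates by term appear nowhere. Confounding by surgery supports a supplementary table without these events, not their removal from the main ones. The SAP itself keeps inhibitor and antibody results from the same periods (8.3.2 and 8.3.3).

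**Conclusion.** The concern holds. Followed as written, SAP 8.2.1 removes a defined set of TEAEs from every detailed AE table while keeping the full denominator. Any-event, SOC/PT, severe, related and SAE incidences can only equal or fall below the all-TEAE values. The severity and relationship profile can look milder or less related than it was.

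The direction follows from the counting rules alone. The size is unknown and may be zero, because the documents give no AE or major-surgery counts; the per-subject weights rest on planned, not actual, sample sizes. No data are lost and the primary endpoint is unaffected. The SAP should be corrected because these tables carry the primary objective, but the point does not threaten the study's main result.

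**What to change.** Replace the sentence in SAP 8.2.1 with:

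> All TEAEs, including those with onset during major surgical/rehabilitation periods, are included in the overall total and in every TEAE, severity, relationship and SAE table for the Safety Analysis Set. The surgery subgroup column is retained. Supplementary tables excluding, and restricted to, major surgical/rehabilitation periods will be provided.

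Revise SAP 8.2 so that AEs starting on the first day of the period or on the day of surgery also appear in the surgical-period summary and in its separate listing. At present only the full AE listing shows and flags them as such.

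The cost is SAP wording and a few more tables, with no new data collection. Any-event, SOC/PT, severe, related and SAE incidences will stay the same or rise; Mild, Moderate and Not-related rows may move either way. The sponsor keeps the separated presentation as a supplement.

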8.2.2. Treatment-emergent Adverse Events

In general, an AE will be regarded as treatment-emergent if it was present prior to receiving the first injection of rFIXFc in the parent study and subsequently worsened in severity, or was not present prior to receiving the first injection but subsequently appeared before the subject's last visit on study or the follow-up phone call, whichever came later (or the date of withdrawal/loss to follow-up).

All AEs that occurred on or after 9HB01EXT Study Day 1 will be considered treatment-emergent in study 9HB01EXT. AEs that were treatment-emergent in the parent studies and carried over to study 9HB01EXT without worsening in severity will be considered the same AEs and will not be counted again in study 9HB01EXT.

The incidence of TEAEs will be summarized by system organ class (SOC) and preferred term. Unless specified otherwise, SOCs and preferred terms within each SOC will be presented alphabetically. For the purpose of summarization, a subject is counted once in a SOC or preferred term if the subject reported one or more events in that SOC or preferred term. Unless specified otherwise, percentages will be based on the number of subjects in the Safety Analysis Set.

8.2.3. Adverse Events in Descending Order of Incidence

A table will be provided which displays TEAE preferred terms in descending order of incidence. Only preferred terms will be included in this table (i.e., the display will not include SOCs).

A similar table will be provided for severe TEAEs. AEs for which the assessment of severity is missing will be included in this table.

8.2.4. Severity of Adverse Events

AEs are classified by the Investigator for severity ("Mild", "Moderate", and "Severe"). A summary of TEAEs by SOC, preferred term, and severity will be presented. AEs with a missing severity will be counted as "Severe" in the summary table. A subject will be counted once for each SOC and preferred term based on the greatest severity within that SOC and preferred term, respectively.

8.2.5. Relationship of Adverse Events to Study Drug

AEs are classified by the Investigator for relationship to study drug ("Not related" and "Related"). A summary of TEAEs by SOC, preferred term, and relationship will be presented. AEs with a missing relationship will be counted as "Related" in the summary table. A subject will be counted once for each SOC and preferred term based on the highest relationship within that SOC and preferred term, respectively.

8.2.6. Serious Adverse Events

Any AE reported as resulting in death, immediate risk of death (life threatening), inpatient hospitalization or prolongation of existing hospitalization, persistent or significant disability/incapacity, or a congenital/anomaly/birth defect will be classified as an SAE by the Investigator. An SAE may also be any other medically important event that, in the opinion of

the Investigator, may jeopardize the subject or may require intervention to prevent one of the other outcomes listed above.

All SAEs will be listed; treatment-emergent SAEs will be summarized by SOC and preferred term.

8.2.7. Adverse Events Leading to Treatment Discontinuation or Withdrawal From the Study

AEs leading to treatment discontinuation or withdrawal from the study will be listed. All AEs reported on the AE log for the item “Was the subject terminated from this study due to this AE” with a response of “Yes” or “Action Taken with Study Drug” with a response of “Drug Withdrawn” will be included.

8.2.8. Deaths on Study

A listing of deaths occurring on study 9HB01EXT will be provided.

8.3. Clinical Laboratory Evaluations

Analyses for laboratory data involving baseline value will be based on study 9HB01EXT Baseline (as defined above in Section 5.1.2).

All laboratory data will be provided in data listings; abnormal values relative to laboratory normal ranges will be identified. Laboratory evaluations taken during major surgical/rehabilitation periods will be included in the listings and flagged.

8.3.1. Hematology and Chemistry

All summaries will be structured such that the hematology and chemistry tests are presented in the order shown in the tables provided in Section 8.3.1. Hematology and chemistry evaluations taken during major surgical/rehabilitation periods will not be included in the summary but will be included in the listings and flagged.

Hematology measurements that will be collected and listed include white blood cell count (WBC), differential, hemoglobin, hematocrit, and platelet count.

Chemistry measurements that will be collected and listed include electrolytes (sodium, potassium, and chloride), glucose, total protein, total bilirubin, alanine aminotransferase (ALT), aspartate aminotransferase (AST), alkaline phosphatase (ALP) [collected for subjects from study 998HB102 only], blood urea nitrogen (BUN), and serum creatinine.

8.3.1.1 Change from Study 9HB01EXT Baseline

Hematology and chemistry results at baseline and post baseline visits, along with change from baseline, will be summarized with descriptive statistics by visit (as defined above in Section 5.1.3) for overall treatment regimen for Safety Analysis Set.

